To assess the efficiency of data linkage between claims data and credit report data and implications for bias based on proportion of total sample that may not have these data [IR-2], data vendor Optum will link patient addresses to geocoded 2000 and 2010 census data, a process that has previously yielded <1% unlinked data. Information on member race and ethnicity is also included, based on geocodes, US census data, and an imputation strategy incorporating member surname. [MD-2] We will also have detailed benefit information for ~80% of employers, including individual and family deductible levels, HDHP type (HSA, Health Reimbursement Arrangement, or non-account), and copay and coinsurance amount by service type. For employers with missing deductible levels, [MD-2] we have developed an imputation algorithm that has 97.0% sensitivity and 96.2% specificity. To determine employer deductible levels, we will use a benefits type variable that we have for smaller employers (with approximately 100 or fewer employees). For larger employers, we will take advantage of the fact that health insurance claims data are the most accurate source for assessing out-of-pocket obligations among patients who utilize health services. Our claims data contain an in-network/out-of-network deductible payment field. For patients who use expensive or frequent services, the sum of their yearly deductible payments will add up to clearly identifiable exact amounts such as \$500.00, \$1000.00, \$2000.00, etc. When several members have these same amounts, it provides strong evidence that the employer offered such an annual deductible level. It will also be possible to detect employers that offer choices of deductible levels when multiple employees have deductibles at two or more levels, such as 20 employees with an annual amount of \$1000.00 and 12 employees with \$500.00. For employers with at least 10 workers, we therefore will sum each employee's in-network deductible payments and number of claims over the enrollment year and plan to assess other key characteristics such as percentage with Health Savings Accounts. On a randomly selected half of the employer data set that contained our calculated employer characteristics (such as the percentage of patients with deductible levels between \$1000-\$2500) as well as actual deductible amounts, we will use a logistic model that predicts the 3-level outcome of deductible <=\$500/\$500-\$999/>\$1000 based on multiple aggregate employer characteristics such as the first and second most common whole number deductible value, the percentage with Health Savings Accounts or Health Reimbursement Arrangements, the median deductible payment, the percentage of employees using services, the employer size, the percentage of employees with deductible levels between \$100-\$500/ \$500-\$1000/ \$1000-\$2500/ >\$2500, etc. This predictive model will output the probability that employers had deductibles in the three categories (summing to 1) and we will assign the employer to the level that had the highest probability. If we detect employers that had 10 or more employees with whole number deductible levels both above and below \$500 (e.g. \$250.00 and \$1500.00), we will assign the employers' category as "choice." If 100% of employees had Health Savings Accounts, we will overwrite any previous assignment to classify the employer as a high-deductible employer. We will test the predictive model on the other half of the sample for which we have actual deductible levels. At employers with 75-100 workers, we anticipate to find sensitivity and a specificity of over 96%. We will have all study years (2004-2014) available in-house. The sample size (see section C.10) will be sufficient to investigate HDHPs' effects within carefully selected employer groups, as well as within vulnerable patient subgroups.

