Member-level Covariates include: bipolar disorder type, age, sex, SES, race/ethnicity, state of residence, rurality, Dartmouth Atlas Hospital Referral Region of residence, baseline out-of-pocket and health plan expenditures, number and month (relative to index date) of outpatient/ED/hospital visits, and enrollment in individual versus family coverage. To derive indicators of race/ethnicity, we will first use a variable supplied by the data vendor that applies surname analysis to categorize members as Hispanic or Asian. We will then use US Census block group data¹¹⁶ (geocoding) to indicate predominantly black or white neighborhoods. We will combine both techniques because geocoding is not sensitive in detecting ethnicity¹¹⁷ and surname analysis is non-informative regarding race. **[MD-2]** This validated approach has a high positive predictive value.¹¹⁸⁻¹²² We will have access to individual-level Credit Report-derived variables for income and net worth, which is a major advance over previous studies that used only neighborhood SES measures. We will also determine neighborhood SES (geocoded poverty and education levels) and use principal components approach to calculate a neighborhood SES index.^{99,123,124,125} Adjusted Clinical Groups scores^{94,95} will estimate comorbidity.

[name]

To account for SES variables' data missingness among HDHP and traditional plan adult members, we will use 3 methods to accommodate missingness: (a) multiple imputation, (b) modeling missingness as a member-level characteristic, and (c) excluding members with missing data. If findings differ, we will present results using all 3 methods in manuscripts or attached appendices. We will use SAS procedures PROC MI and PROC MIANALYZE to impute the missing individual level covariates and conduct the statistical analyses under the assumption of missing at random. The SAS procedure PROC MI will impute the missing variables (including individual net worth, income level, poverty level and education level) using other available variables such as age, gender, census block level income, poverty, education and etc. Then we will use PROC MIANALYZE to analyze the imputed data. We will also explore certain Bayesian imputation techniques to handle missing data in case missing is not at random and compare the results.^{146,147}

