(Aim 3) Patient Out-of-Pocket Costs Burden: Analysis of changes in patient costs will rely primarily on a pre-post with propensity-matched comparison group design and a difference-in-differences analytical framework. We will model costs to patients using two-part general linear models. We will select the conditional mean and variance functions based on the actual data, potentially using a log link with a Gamma error distribution.^{127,128} To inform the final model specification, we will employ specification tests including the Pregibon Link test for non-linearity¹²⁹ and a modified Park test to select the conditional variance function.¹²⁷

Stratified Analyses to Assess Effects on Vulnerable Subgroups: We will compare outcomes between HDHP and traditional plan members among strata defined by four covariates: comorbidity burden (e.g., higher versus low tertiles of Adjusted Clinical Groups score,^{81,82} SES (higher versus low tertiles); race/ethnicity (non-Hispanic white versus black, Asian, Hispanic, and other), and rural versus urban residency. We will use GEE or GLMM to express relative changes in outcomes among HDHP member subgroups compared to changes among controls.¹³⁰ If statistical power permits, we will add three-way interaction terms (e.g. study_group*study_period*SES) to assess whether the HDHP switch was associated with a change in baseline disparities in outcomes.

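### The predictors named for imputing individual SES leave out plan cohort and outcomes; an imputation limited to them would shrink the multiple-imputation estimate of the SES-by-HDHP effect

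*Combined protocol and SAP*

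**What the plan says.** Section C.8 (Covariates for Aims 1-3) imputes several SES measures, "including individual net worth, income level, poverty level and education level", with PROC MI and PROC MIANALYZE "under the assumption of missing at random". The imputation is to be done "using other available variables such as age, gender, census block level income, poverty, education and etc".

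Multiple imputation is one of three planned approaches: "a) multiple imputation, (b) modeling missingness as a member-level characteristic, and (c) excluding members with missing data". None is called primary. The reporting rule is: "If findings differ, we will present results using all 3 methods in manuscripts or attached appendices". Departures from missing at random get an exploratory step: "We will also explore certain Bayesian imputation techniques to handle missing data in case missing is not at random and compare the results".

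SES is more than an adjustment variable. The subgroup paragraph of C.5 gives, as an example, a comparison of the top and bottom thirds of household income. The stratified-analysis paragraph of C.9 compares plan groups within SES strata and, if power is adequate, adds "three-way interaction terms (e.g. study_group*study_period*SES) to assess whether the HDHP switch was associated with a change in baseline disparities in outcomes". The limitations section also lists SES among the variables used for individual matching.

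No missing rate for individual income or net worth is given. The one linkage figure, in C.2, is "a process that has previously yielded <1% unlinked data". It describes linking addresses to geocoded census data, not how complete the credit-report variables are.

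**The concern.** An imputation model should contain the variables of the analysis it feeds, including the outcome and any interaction to be estimated. Here the analysis asks whether the change after the switch differs by SES between HDHP members and controls. If a member's income is drawn from age, sex and neighbourhood alone, the drawn value is unrelated to how that member responded to the switch, except through what neighbourhood says about income. Members with imputed SES then dilute the contrast, and the estimate moves toward no difference. This happens even when the missing-at-random assumption is correct.

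At stake is whether poorer patients are harmed more by HDHPs. Poorer patients are one of the named vulnerable subgroups in Aims 1-3, and outcome disparities have their own manuscript in the timeline.

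**Working it through.** The plan states no SES missing rate, no measure of how well the predictors explain income, and no power for an SES interaction, so there is no figure of its own to reproduce. The subgroup power figure in C.10 concerns non-white members and does not bear on this point.

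**Inputs**
- From the plan: 10,800 HDHP members and 43,200 controls (C.10), a 1:4 ratio; the named predictors (C.8); SES as effect modifier (C.5, C.9).
- Assumed: missing share m from 5% to 40%; R² of individual income on the named predictors from 0.1 to 0.5.

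**Formula.** Let β be the true SES-by-HDHP effect per unit of SES. Among members with observed SES the slope is β. Among members whose SES is drawn only from area-type predictors, and where those predictors affect the outcome only through SES, the slope is R²β. Weighting by share:

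(1 − m)β + mR²β = β[1 − m(1 − R²)]

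At m = 0.10: 1 − 0.10 × 0.9 = 0.91 (R² = 0.1) and 1 − 0.10 × 0.5 = 0.95 (R² = 0.5). At m = 0.40: 1 − 0.40 × 0.9 = 0.64 and 1 − 0.40 × 0.5 = 0.80. At m = 0.05 the range is 0.955 to 0.975.

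**Simulation.** This used a difference-in-differences on change scores with 2,700 HDHP members and 10,800 controls (one quarter of the planned size), missingness depending on the area variable, 40 replicates and 3 imputations. Entries are the share of the true interaction recovered, over R² of 0.1 to 0.5. With no missing data the share was 0.98 to 1.01.

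| Missing | Formula | MI, area variables only | MI, cohort and outcome added, no product | MI, cohort × outcome included | Complete case |
|---|---|---|---|---|---|
| 10% | 0.91–0.95 | 0.90–0.95 | 0.90–0.95 | 0.99–1.01 | 0.99–1.01 |
| 20% | 0.82–0.90 | 0.80–0.90 | 0.81–0.90 | 0.97–1.00 | 0.99–1.00 |
| 30% | 0.73–0.85 | 0.73–0.84 | 0.72–0.85 | 0.98–1.00 | 0.99–1.01 |
| 40% | 0.64–0.80 | 0.63–0.80 | 0.63–0.81 | 0.95–1.01 | 0.97–1.00 |

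A contrast of the highest with the lowest tertile lost about the same (0.64 to 0.95 of the full-data value kept).

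**Threshold effect.** The effect was also confined to the lowest third: a change of −3 in low-income and −1 in other HDHP members, so a true excess of −2, with 20% in HDHPs and a correlation of 0.3 to 0.6 between individual and block income. Imputing from block income alone kept 89–93% at 10% missing and 62–70% at 40%; further runs near 40% went down to 59%. At 62–70%, an excess of −2 would be reported as −1.24 to −1.40. Normal-model imputation within cohort, with outcomes, recovered only 81–95%. Imputing the tertile itself by a logistic model within cohort recovered 99.5–102%.

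**Price of complete case.** Of 10,800 + 43,200 = 54,000 members, 10% missing drops 5,400 and 40% drops 21,600. Standard errors grow by about 1/√(1 − m): 1.05 at 10% and 1.29 at 40%.

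**The case against.** The strongest reply is that this is an under-specified step, not an error. The wording of the predictor list marks it as examples, so cohort and outcomes are not excluded. A reader might infer that the plan leaves them out by design; the text does not support that.

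A reader might also infer that the whole disparity answer is biased toward no difference. That too goes beyond the documents. The attenuation belongs to one of three estimates. Complete case was essentially unbiased when missingness depended on the area variable, and all three sets of results are to be shown if they differ. The missing-indicator method was not evaluated here. The SES stratifier is not fixed either: household income is only an example, C.8 also builds a neighbourhood index that would be almost complete, and the three-way term is conditional on power.

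These replies limit the point but do not remove it. The only predictors named are ones that do not protect the interaction, and adding cohort and outcome without their product gained nothing. The reporting rule does not define what counts as a difference or which result then prevails, so a reader could trust multiple imputation as the fuller analysis when it is the attenuated one. The Bayesian step addresses data not missing at random, whereas this bias arises under missing at random.

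**Conclusion.** The point holds conditionally. If the imputation uses only the kinds of variable named, the multiple-imputation estimate of the SES-by-HDHP effect is too small by about m(1 − R²): some 3 to 5% at 5% missing, 5 to 10% at 10%, and roughly 20 to 40% at 40%. These sizes rest on assumed missing shares and R², and the documents do not show which case applies. In particular, the census-linkage figure cannot be used to argue that the loss is negligible, and nothing in the plan shows that it is large. The finding that complete case is not attenuated rests on missingness depending only on the area variables. The change is worth making before the SES analyses are run, because the imputation model decides how far the multiple-imputation answer can be believed.

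**What to change.** For the SES-stratified and three-way analyses:

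- Impute SES separately within each plan cohort, or include cohort-by-outcome products. Use outcomes before and after the switch and all analysis covariates as predictors. Where HSA-eligible and HSA-ineligible members are contrasted, treat them as separate cohorts.
- Impute on the scale analysed, for example the tertile by a logistic model.
- Keep a separate imputation, without follow-up outcomes, for the propensity match.
- Report SES missingness by cohort, name the primary missing-data method in advance, and show the complete-case estimate beside the multiple-imputation estimate in every case, not only when findings differ.

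The cost is programming and a paragraph of text, since the claims data are retrospective. It is more than adding two variables. The outcomes include monthly series, binary measures, counts and costs, so the imputation models become outcome-specific. Two sets of imputed SES values must be maintained, and a member may carry one value for matching and another for stratification, which the plan should acknowledge.

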Study cohort: Of 41,638,597 members enrolled in the national insurer during 2004-2012, we found 18,184,556 have a 2-year enrollment span, a study inclusion criterion. Among these, 148,706 have at least 1 inpatient or 2 outpatient diagnoses of bipolar disorder; this reflects a prevalence of 1% members with bipolar disorder, which is consistent with expectation among the commercially insured population. Among 148,706 members with bipolar disorder, 57,028 matched our age criterion (12 to 64 years of age). (We will conduct sensitivity analyses of our main results varying our bipolar diagnosis criteria [e.g., requiring diagnosis prior to index date, requiring only one diagnosis; [CI-5](#)]) To minimize selection bias, our study cohorts will include individuals whose employers offer only a single benefit type with no choice. Our intervention cohorts will include traditional plan members with bipolar illness who experience an employer-mandated switch to HSA-eligible HDHPs with full drug cost-sharing (i.e., out-of-pocket medications payments until the deductible limit is reached), or to HSA-ineligible HDHPs that subject medications only to copayments as in traditional health plans. The control cohort will include members with bipolar illness whose employers offered only a traditional plan for the follow-up year. We estimate that 7,227 have HDHP insurance and 49,801 have traditional plan insurance. **Exclusion Criteria:** We will exclude members age 65 years or older who could be eligible for Medicare benefits, including drug coverage through Medicare Part D. We will also exclude members whose employer offered a choice of health plan. This strengthens our design by reducing potential selection bias due to, for example, healthier members selecting HDHPs or individuals anticipating discretionary utilization. . Input from our panel advisory meetings led to the decision to exclude from our cohort those individuals with a diagnosis of schizoaffective disorder or schizophrenia in order to identify a clinically homogenous group for our study, as advised by our clinical psychiatrist co-investigator [name]. This criterion was further supported by our advisors at DBSA. According to sources at DBSA, schizophrenia and schizoaffective disorder are not comorbidities seen in their peer population. In their judgment, people living with schizophrenia and schizoaffective disorder are unlikely to come to DBSA meetings and would have their needs better met in other settings. The ineligibility criteria therefore included the 3 categories: 1) patients with only 1 outpatient bipolar diagnosis, 2) 1 inpatient or 2 outpatient diagnosis of schizophrenia diagnosis, and 3) 1 inpatient or 2 outpatient diagnosis of schizoaffective disorder. We estimate 3,731 individuals were excluded from the study cohort due to evidence of schizoaffective disorder and schizophrenia. There have been no changes in identifying eligible individuals to enroll in our approved research plan beyond the stakeholder advisory panel decision to exclude schizoaffective disorder and schizophrenia, calculate their overlap with the bipolar population, and exclude them from the final cohort.

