Employer-level Propensity Matching: The study population will include employees of firms that mandated a switch to HDHPs and others that kept traditional plans as their sole insurance option. While this minimizes member-level selection into health plans, our previous work indicates that some employers might select HDHPs based on employee characteristics.¹⁰⁰ To create strata of employers with similar baseline characteristics, we will generate scores predicting the propensity of an employer switching to an HDHP in a given year among all employers making such a decision. Propensity scoring is a well-established method that assists in generating a comparison group with a similar likelihood of being exposed to a given “intervention” (in this case, shifting to HDHP coverage) based on measured characteristics when subjects have not been randomly allocated into study groups.¹⁰¹⁻¹⁰⁴ We will use logistic regression to predict an employer’s likelihood of switching to an HDHP (versus remaining in a traditional plan). Candidate predictors in our propensity score models will include baseline employer-level covariates (Section C.8). We will use results from this model to divide employers into four strata according to propensity score, then match HDHP members with bipolar illness to traditional plan members with bipolar illness within each stratum (see immediately below).¹⁰⁴

Individual-level Propensity Matching: To identify closely matched patient controls for each of our HDHP study members with bipolar illness, we will use member-level propensity score matching¹⁰¹ to select members within the eligible pool of employees from each stratum of matched employers. Based on individual-level covariates (Section C.8) and similar enrollment dates, we will match four contemporaneous controls with bipolar disorder to each HDHP member with bipolar disorder within a pre-defined propensity score caliper (0.6 of the standard deviation of the pooled baseline propensity score).¹⁰⁵

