(Aim 3) Patient Out-of-Pocket Cost Burden: We will examine annual patient out-of-pocket costs (paid deductible, coinsurance, and copayment amounts), summing these discretely for prescription fills, outpatient visits, and other major service categories. We will calculate both the overall annual burden of costs per patient, and measures such as average cost per fill or per month of medication, and per behavioral health visit, which may be easier for lay consumers of our research results to consider and compare. To control for price inflation, we will convert all patient costs to current year US dollars using the Consumer Price Index.¹¹⁵

C.8 Covariates for Aims 1-3: We will use (i) employer-level and (ii) individual-level covariates to propensity match, adjust, or stratify our analyses.

Employer-level Covariates include: employer size, health plan expenditure quintile, employee out-of-pocket cost quintile, median employee age, median employee comorbidity score, and proportions of employees who are women, have family coverage, and reside in high-poverty or low-education neighborhoods. Our ongoing research has found that health plan and employee out-of-pocket costs independently predict employer HDHP enrollment. We will calculate baseline expenditures by summing standardized amounts paid by the health plan for all services utilized by all employees; the data vendor provides these standardized cost amounts. We will use median employee Adjusted Clinical Groups scores^{94,95} to estimate comorbidity; the ACG algorithm uses age, sex, and ICD-9-CM codes to calculate a morbidity score relative to a reference population average of 1.0.⁹⁴ Researchers have validated the index against premature mortality.⁹⁵

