C.9 Analysis Plan for Aims 1-3 [IR-3; HT-1 to HT-4]: Overview: These analyses will determine how specific outcomes change after employer-mandated switching from traditional plans to HDHPs. To address methodological standard IR-3, we plan to use the most rigorous quasi-experimental retrospective longitudinal designs and analyses available for AIMS 1-3, namely interrupted time series with comparison series matched on multiple baseline covariates as well as the baseline trend of outcome measures. For Aim 4 we will use appropriate standard techniques for qualitative analyses of interview data (detailed below). We will first compare the characteristics of our matched cohorts (HSA-eligible and HSA-ineligible HDHP members, and traditional plan controls) using chi-square tests, t-tests and Poisson or quantile regression.¹²⁶ We will contrast sociodemographic characteristics, employer characteristics, and baseline health care utilization. Subsequent analyses will use time-series plots and rigorous analytical methods appropriate for each outcome, described below. Data collected on the same individuals in successive years are correlated (“repeated observations”). The extended general linear models—generalized estimating equations (GEE) and generalized linear mixed models (GLMM) for binary, count, or continuous measured outcomes—are appropriate methods for estimating parameters to adjust for these correlations within subjects.^{82,83} The term of interest in our GEE or GLMM models will be the interaction between *time* (pre versus post) and *cohort* (HDHP versus traditional plan). Statistical analyses in Aims 1-3 will first compare those transitioning to HDHPs with patients remaining in traditional plans; then contrast effects between HDHP members with full drug cost-sharing (HSA-eligible plans) and those transitioning to HDHPs without full drug cost-sharing (HSA-ineligible HDHPs). Each HDHP group will have as controls only those traditional plan members paired to a given HDHP member during the propensity score match. To examine possible selection effects due to applying our enrollment criteria and propensity matching approaches (see C.10), we will also compare our analytic population to members with bipolar disorder who were excluded from the sample.^[MD-4; CI-2]

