(Aim 1) Access to Appropriate Outpatient Care: We will assess changes before and after the index month in the *utilization and adherence* outcomes listed in C.7 for Aim 1 using patient-level *interrupted time series with comparison series*. The interrupted time series design includes multiple observations over time both before and after an intervention (i.e., the plan switch) and adjusts for most threats to internal validity (e.g., secular changes in prescribing, aging of the population) because it adjusts for baseline trends in study outcomes that are unrelated to the intervention.⁸⁰ Furthermore, our strategy of matching on the baseline outcome trend should generate highly robust causal estimates. We will use patient-level segmented linear regression models^{58,84} to statistically estimate patient-level changes in both level and trend in outcomes after the switch to HDHPs, while controlling for autocorrelation of the data and individual-level covariates. The segmented regression models include a constant term; an integer variable indicating *time* in months (t) from the start of the observation period to estimate baseline trend; a binary variable, *intervention*, indicating the period after the index month, to estimate change in level; and an interaction between *intervention* and *time*, to estimate change in trend. We will test the statistical significance of level or trend changes, adjusting for first-order autocorrelation between sequential monthly measurements using the empirical sandwich estimator in GEE.⁵⁸

For selected quality measures (i.e., likelihood of a quarterly outpatient mental health visit or receiving

guideline-recommended lab monitoring when using lithium, valproate, carbamazepine, and 2nd generation antipsychotics; C.7), our approach will be a pre-post with comparison group and difference-in-differences design. Logistic regression models will assess the independent effect of HDHPs on these outcomes, while controlling for patient-level covariates and secular utilization trends (by including index month).^{54,55,99}

(Aim 2) Adverse Patient Clinical Outcomes: To examine the impact of transitioning to HDHPs on changes in rates or risk of psychiatric/non-psychiatric ED visits and hospitalizations, we will use a pre-post with comparison group difference-in-differences design. We will control for patient-level covariates in the models. We will use GLMM to model the effect of HDHPs on annual hospitalization days.

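### Plan type is assigned by employer, but the analysis plan specifies correlation only within patients, so standard errors are too small if coworkers' changes are positively correlated

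*Combined protocol and SAP*

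**What the plan says.** Exposure is set by the employer. Section C.5 (Study cohort) restricts the cohorts to "individuals whose employers offer only a single benefit type with no choice", and C.6 models each employer's propensity to switch. All cohort members at one firm therefore share the same exposure in a given year.

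Dependence is described in C.9 as follows:

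- **Overview.** Repeated observations on the same person are correlated, and GEE and GLMM are "appropriate methods for estimating parameters to adjust for these correlations within subjects".
- **Aim 1, segmented regression.** Level and trend changes are tested "adjusting for first-order autocorrelation between sequential monthly measurements using the empirical sandwich estimator in GEE". The cluster unit of that estimator is not named.
- **Aim 1, quality measures.** "Logistic regression models will assess the independent effect of HDHPs on these outcomes, while controlling for patient-level covariates". No cluster is named.
- **Aim 2.** "We will use GLMM to model the effect of HDHPs on annual hospitalization days". The level of the random effect is not stated, so an employer effect is neither included nor ruled out.
- **Aim 3.** "We will model costs to patients using two-part general linear models". No cluster is named.

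The employer appears in two other places. Section C.6 uses the employer propensity model to "divide employers into four strata according to propensity score" and matches patients within those strata. Section C.8 lists "employer-level and (ii) individual-level covariates to propensity match, adjust, or stratify our analyses". Section C.10 gives no number of employers, no patients per employer, no ICC and no design effect. Its correlation of 1 refers to repeated observations on a patient, not to coworkers.

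**The concern.** When exposure is assigned to groups, the precision of the effect estimate depends on how much outcomes vary between groups, not only between people. A difference-in-differences contrast removes stable differences between employers. It does not remove changes specific to one employer between the baseline and follow-up years, such as a change in network or in other benefits. Out-of-pocket cost is the clearest case. C.2 describes deductibles, copayments and coinsurance as employer-level benefit information, so coworkers are likely to share part of the Aim 3 change.

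Two conditions must both hold for harm: some employers contribute more than one cohort member, and pre-post changes are positively correlated within employers. If so, patient-level standard errors are too small, intervals too narrow and the type I error above 5%. If either fails, there is no inflation. Most exposed would be comparisons drawn from few employers. The HSA group, at 1525 members in C.10, could be one, but its number of employers is not given.

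**Working it through.** **1. The plan's own power figure.** Inputs from C.10: 2160 non-white HDHP members, 8640 matched controls, 10% baseline psychiatric hospitalization, a fall to 8%, alpha 0.05, power 80%. Sidedness is not stated; two-sided is assumed. Treat patients as independent, with one effective observation each.

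- Pooled proportion: (2160 × 0.08 + 8640 × 0.10) / 10,800 = 0.096.
- Null SE: √[0.096 × 0.904 × (1/2160 + 1/8640)] = 0.00709.
- Alternative SE: √[0.08 × 0.92/2160 + 0.10 × 0.90/8640] = 0.00667.
- Power: Φ[(0.02 − 1.96 × 0.00709) / 0.00667] = 82.0%, or 80.9% with continuity correction.

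The stated figure thus reproduces as a comparison of independent patients. The exact PASS procedure is not stated.

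**2. Design effect at which this power reaches 80%.** Multiplying both variances by a design effect (DE) gives 80% at DE = 1.05, or 1.02 with continuity correction. This applies to the smallest subgroup and least frequent outcome. For the whole projected cohort (10,800 against 43,200), the same formula stays above 80% until DE is about 5.3 (5.2 with continuity correction).

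**3. Patients per employer.** The documents do not give this. A rough ratio from C.5 is 57,028 / 18,184,556 = 0.31%, that is 0.3 expected cohort members per 100 enrolled people and about 3 per 1,000. Its limits:

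- The denominator counts members, including dependents, and is not limited to single-plan employers.
- C.2 counts employees when it discusses firms of about 100, so employees and members are not the same unit.
- With 1:4 matching, at most 4 × 7,227 = 28,908 of 49,801 controls (58%) are used, so control clusters would be smaller.

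**4. Consequence for the tests.** Formulas, for mean cluster size m and coefficient of variation CV:

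- Equal clusters: DE = 1 + (m − 1) × ICC.
- Unequal clusters: DE = 1 + [(1 + CV²) × m − 1] × ICC.
- True size of a nominal 5% test: 2 × [1 − Φ(1.96/√DE)].
- The correct interval is wider by a factor √DE.

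The ICC is that of the pre-post change. All m, CV and ICC values below are assumptions.

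| m | CV | ICC | DE | True size | Interval factor |
|---|---|---|---|---|---|
| 1 | 0 | any | 1.00 | 5.0% | 1.00 |
| 3 | 0 | 0.01 | 1.02 | 5.2% | 1.01 |
| 3 | 0 | 0.05 | 1.10 | 6.2% | 1.05 |
| 3 | 0.5 | 0.01 | 1.03 | 5.3% | 1.01 |
| 3 | 0.5 | 0.05 | 1.14 | 6.6% | 1.07 |

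**5. Larger clusters, as a check on the mechanism.** At ICC 0.05, m = 10 gives DE 1.45 and a size of 10.4%; m = 20 gives DE 1.95 and 16.0%. A simulation with employer-level exposure and 2160 against 8640 patients (3,000 runs per setting) gave rejection rates of 10.0% and 17.1% with patient-level errors, against 4.8% and 5.5% with employer-clustered errors. At the 0.31% ratio, these cluster sizes need employers with about 3,200 to 6,400 enrolled people. Nothing in the documents shows how common those are, so these rows show what clustering does, not what to expect here.

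**The case against.** The strongest reply is that the effect may be trivial. A cohort drawn from a less common condition may include few patients per firm, and the central assumed settings inflate the test size by only 0.2 to 1.6 percentage points. That stands as a limit on size. It does not show that cluster sizes are near one: C.2 distinguishes firms of about 100 or fewer employees from larger ones, and no cap on firm size is stated.

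The power threshold is also a worst case. If non-white members are spread evenly, a 1,000-person employer has about 0.2 × 3.14 = 0.63 of them. With Poisson cluster sizes, DE = 1 + 0.63 × ICC, or 1.006 to 1.03 at an ICC of 0.01 to 0.05. Power is then 80.8% to 81.8%, or 79.6% to 80.6% with continuity correction. This also stands: the power claim is not shown to fail.

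Adjusting for employer covariates, which C.8 permits, could explain some shared variation and lower the residual ICC. That is fair, but matching and covariate adjustment do not correct the variance for the correlation that remains.

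Two narrower points also hold. The GEE passage names no cluster unit, so reading it as the patient is an inference, though a natural one given the within-subject wording. And a benefit change common to all switching employers would bias the estimate itself, which clustered errors would not cure.

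**Conclusion.** The concern holds in conditional form. The employer assigns exposure, while the plan specifies only within-patient dependence and allows for no employer clustering in the variance or the power. Followed as written, the analysis understates uncertainty wherever employers contribute several patients with positively correlated changes.

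The size is unknown. It is nil with one patient per employer or a zero ICC. In the assumed settings of three patients per employer and an ICC of 0.01 to 0.05, the true size is 5.2% to 6.6% and correct intervals are 1% to 7% wider, taking equal and moderately unequal clusters together. Larger or more uneven clusters would raise this. The Aim 2 subgroup power has little reserve, but it is not shown to fall short. This should be fixed because the remedy is cheap and the present specification does not match the unit of assignment.

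**What to change.** - In all Aim 1-3 and subgroup models, name the employer as the cluster for the empirical sandwich variance. This also covers within-patient correlation while a patient stays with one employer.
- For the GLMM, state the level of the random effects and use employer-clustered empirical standard errors.
- Apply a small-sample correction if an arm, such as the HSA group, comes from few employers.
- Report employers per arm, the distribution of cohort members per employer, and the estimated ICC of the change.
- In C.10, state that the Aim 2 power assumes no employer clustering, or restate it with the observed design effect.

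The cost is small. For the GEE, logistic and two-part models it is a change of cluster variable, using an identifier that the C.6 matching already needs. The GLMM needs one added specification, and the power statement one recalculation. Intervals may widen somewhat; if clustering is negligible, they will barely move.
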